10.3 Clinical laboratory evaluations

The list of the laboratory measurements/variables that will be evaluated in the study is specified in Table 10-1 per laboratory category.

Table 10-1: Laboratory measurements

Hematology	Biochemistry	Urinalysis
Basophils	Calcium	pH
Eosinophils	Chloride	Albumin (protein)
Lymphocytes	Magnesium	Glucose
Monocytes	Potassium	Blood
Neutrophils	Sodium	Leukocyte esterase
Hematocrit	Glucose	Nitrite
Hemoglobin	BUN	Urine dipstick for pregnancy testing
MCH	Creatinine	Urine drug screen
MCHC	AST	
MCV	ALT	
Platelet count	ALP	
RBC count	GGT	
WBC count	Total bilirubin	
	LDH	
	Total cholesterol	
	Serum pregnancy testing	

Hematology	Biochemistry	Urinalysis
	hs-CRP	
Hematology	Biochemistry	Urinalysis
Basophils	Calcium	pH

ALP=alkaline phosphatase; ALT=alanine aminotransferase; AST=aspartate aminotransferase; BUN=blood urea nitrogen; hs-CRP=high sensitivity C-reactive protein; ET=early termination; GGT=gamma-glutamyltransferase; HDL=high density lipoprotein, IMP=investigational medicinal product; LDH=lactate dehydrogenase; MCH=mean corpuscular hemoglobin; MCHC=mean corpuscular hemoglobin concentration; MCV=mean corpuscular volume; RBC=red blood cell; SFU=Safety Follow-Up; WBC=white blood cell.

The laboratory analyses will mainly be prepared using data from the central laboratory, except for determining treatment-emergent abnormal values, potential drug-induced liver injury or potential Hy's Law cases. In the latter cases, both central and local laboratory results can be used if the local laboratory values meet specific criteria detailed thereafter:

- The local laboratory value should not be considered without a provided local laboratory range in the database on the local laboratory CRF page,
- The local laboratory value should have been reviewed and checked,
- Only local laboratory results coming from the same assessment and laboratory at the exact same time point can be used for the determination of potential drug-induced liver injury or potential Hy's law criteria,
- Local laboratory values which are not reported in standard international (SI) units will need to be converted in SI units prior to inclusion in the statistical analyses,
- An indicator will be added in the table summaries and study participant listings when local laboratory contributed to the displayed results.

All laboratory summaries will be presented in SI units and will be based on observed case values. In the case where laboratory values are below the lower limit of quantification, then these will be set to the midpoint between 0 and the lower limit of quantification for the purpose of summarizing the data.

The following two summary statistic tables will be created for all laboratory continuous variables (unless otherwise notified). These two tables will be provided on the SS for the overall period, presenting the Placebo/BKZ 160mg Q4W and the BKZ 160mg treatment columns. Baseline will correspond to the original Baseline Day 1.

- A summary of the absolute and change from Baseline values in each laboratory variable by treatment group and visit.
- A summary of the number and percentage of study participants with a given common terminology criteria for adverse events (CTCAE) grade (0, 1, 2, 3 or 4) based on the minimum/maximum post-Baseline value, by laboratory variable and treatment group.

This analysis will be restricted to the hematology and biochemistry laboratory parameters only, and will include the following parameters: hemoglobin, platelet count, WBC count, lymphocytes, neutrophils, creatinine, sodium, potassium, calcium, magnesium, total cholesterol, total bilirubin, AST, AST and GGT.

The hs-CRP parameter will not be included in the summary statistics on absolute and change from Baseline values because the results are already planned to be presented as part of an efficacy analysis (see Section 8.3.1.5).

As indicated in Section 3.1, for tables where data are summarized by visit only values occurring at scheduled visits will be included.

A shift table of the number and percentage of study participants with a given CTCAE grade 0, 1, 2, 3 or 4 values (as applicable) at Baseline to minimum/maximum post-Baseline CTCAE grade, by laboratory variable and treatment group will additionally be created for the hematology and biochemistry laboratory parameters only. The analysis will be performed for the following parameters: hemoglobin, platelet count, WBC count, lymphocytes, neutrophils, creatinine, sodium, potassium, calcium, magnesium, total cholesterol, total bilirubin, AST, ALT and GGT.

In addition, a summary table of the number and percentage of study participants experiencing markedly abnormal values by laboratory variable, treatment group and visit will be created for biochemistry, hematology and liver function test values.

Markedly abnormal values are defined as those with a severity of Grade 3 and above based on the CTCAE criteria Version 4.03. Definitions of markedly abnormal values using the Grade 3 cut points are given in [Table 10–2](#), [Table 10–3](#) and [Table 10–4](#) in order to allow for a more thorough review of elevated LFTs.

All values observed at any time while on treatment (ie, occurring at scheduled and unscheduled visits) will be included in this table summarizing markedly abnormal values. For this summary, Baseline values and values observed more than 140 days after the last administration of study medication are not considered.

This document cannot be used to support any marketing authorization application or variations thereof.

Table 10–2: Definitions of markedly abnormal biochemistry values

Parameter name	Unit	Criteria	Abnormal designation
Creatinine	mmol/L	>3.0 x Baseline or >3.0 x ULN	AH
Glucose	mmol/L	<2.2	AL
		>13.9	AH
Calcium	mmol/L	>3.1	AH
		<1.75	AL
Magnesium	mmol/L	>1.23	AH
		<0.4	AL
Potassium	mmol/L	>6.0	AH
		<3.0	AL
Sodium	mmol/L	>155	AH
		<130	AL
Cholesterol	mmol/L	>10.34	AH

AH=abnormal high; AL=abnormal low; dL=deciliter; L=liter; mg=milligram; mmol=millimoles; ULN=upper limit of normal.

Table 10–3: Definitions of markedly abnormal hematology values

Parameter name	Unit	Criteria	Abnormal designation
Hemoglobin	g/L	<80	AL
		>40 above ULN	AH
Lymphocytes Absolute	$10^9/L$	<0.5	AL
		>20.0	AH
Neutrophils Absolute	$10^9/L$	<1.0	AL
Platelets	$10^9/L$	<50	AL
WBC/ Leukocytes	$10^9/L$	<2.0	AL
		>100	AH

AH=abnormal high; AL=abnormal low; dL=deciliter; L=liter; mg=milligram; mmol=millimoles; ULN=upper limit of normal.

Table 10-4: Definitions of markedly abnormal liver function values

Parameter name	Unit	Criteria	Abnormal designation
Alkaline Phosphatase	U/L	>5.0 x ULN	AH
ALT	U/L	>5.0 x ULN	AH
AST	U/L	>5.0 x ULN	AH
Total Bilirubin	umol/L	>3.0 x ULN	AH
GGT	U/L	>5.0 x ULN	AH

ALT=alanine aminotransferase; AST=aspartate aminotransferase; GGT=gamma-glutamyltransferase

Another table will list the count and percentage of study participants meeting the below criteria at any time during the study while on treatment:

- AST: >2xULN, >3xULN, >5xULN, >10xULN, >20xULN
- ALT: >2xULN, >3xULN, >5xULN, >10xULN, >20xULN
- AST or ALT: >2xULN, >3xULN, >5xULN, >10xULN, >20xULN
- Bilirubin: >1xULN, >1.5xULN
- ALP: >2xULN

In addition, a table will be produced to summarize potential Hy's Law cases. The following two definitions will be used in that table:

- [AST \geq 3xULN or ALT \geq 3xULN] and Total Bilirubin \geq 2xULN
- [AST \geq 3xULN or ALT \geq 3xULN] and Total Bilirubin \geq 2xULN in the absence of ALP \geq 2xULN

Neutrophil values for study participants with at least one treatment emergent markedly abnormal neutrophil value will be plotted over time.

A spaghetti plot will be created for ALT values for study participants with at least one treatment emergent markedly abnormal ALT value. The plot will also be created for AST values.

Results for the shift tables, the graphs and summary tables on markedly abnormal values and the Hy's Law cases tables will be presented as follows:

- on the SS for the Double-Blind Treatment Period for the Week 24 interim analysis only, presenting the Placebo and BKZ 160mg treatment columns,
- on the MS for the Maintenance Period for the Week 52 interim analysis only, presenting the BKZ 160 mg Total treatment column only,
- on the SS for the overall period, presenting the BKZ 160 mg Total treatment column only.

For the two last analyses presenting data occurring during the Maintenance Period, Baseline Week 16 will be used as Baseline for study participants randomized to Placebo that switched to bimekizumab at Week 16.

A by-study participant listing of all laboratory data (excluding urinalysis results) will be provided. In this listing, values that are out of normal range will be flagged (abnormal values that

are below the lower limit of the reference range flagged as 'L' (low) and abnormal values that are above the upper limit of the reference range flagged as 'H' (high)).

In addition, the laboratory results classified as Grade 3 or Grade 4 will be listed separately.

Urinalysis laboratory results will be listed separately, as well as all additional laboratory samples that may have been collected for a study participant.

An additional listing will be created for study participants with suspected hepatic events.

10.4 Vital signs, physical findings, and other observations related to safety

10.4.1 Vital signs, weight and physical findings

The following results will be tabulated for the vital sign variables (systolic blood pressure (mmHg), diastolic blood pressure (mmHg), and pulse rate (beats/min)), by treatment group and visit:

- A summary of the absolute and change from Baseline value

The table will be done on the SS, will cover the overall period, and present the Placebo/BKZ 160mg Q4W and the BKZ 160mg treatment columns.

- A summary of the number and percentage of study participants experiencing at least one markedly abnormal value for a vital sign variable as defined in [Table 10–5](#) below.

The table will be presented:

- on the SS for the Double-Blind Treatment Period for the Week 24 interim analysis only, presenting the Placebo and BKZ 160mg treatment columns.
- on the MS for the Maintenance Period for the Week 52 interim analysis only, presenting the BKZ 160 mg Total treatment column only.
- and on the SS for the overall period, presenting the BKZ 160 mg Total treatment column only.

For the two last analyses presenting TEMA data occurring during the Maintenance Period, Baseline Week 16 will be used as Baseline for study participants randomized to Placebo that switched to bimekizumab at Week 16.

Table 10–5: Definitions of markedly abnormal blood pressure values

Parameter (unit)	Markedly abnormal low	Markedly abnormal high
Systolic blood pressure (mmHg)	<90 and a decrease from Baseline of ≥ 20	>180 and an increase from Baseline of ≥ 20
Diastolic blood pressure (mmHg)	<50 and a decrease from Baseline of ≥ 15	>105 and an increase from Baseline of ≥ 15

At Visit 2, vital signs are planned to be assessed three times (prior to the study treatment administration, 30 minutes after the study treatment administration and 1 hour after the study treatment administration). Baseline will be defined as the last available value up to and including the assessment collected at Visit 2 prior to first dose.

At Week 16, vital signs collected before IMP belong to the double-blind treatment period, while vital signs collected after IMP belong to the maintenance period.

A by-study participant listing of all vital sign results (including body temperature) with the details of abnormalities (when applicable) will be provided (abnormal values will be flagged as “L” or “H” accordingly).

Similarly, physical examination findings together with the details of abnormalities (when applicable) will be listed by treatment group, study participant and visit.

Body weight will also be listed.

10.4.2 Electrocardiograms

Since it is only planned to assess electrocardiogram (ECG) at the Screening Visit, the Baseline value will be derived based on the Screening assessment.

The date and time of the ECG will be recorded in the eCRF together with the Investigator interpretation. A summary of the number and percentage of study participants with normal, abnormal not clinically significant, and abnormal clinically significant ECG results will be presented for Baseline and post-Baseline timepoints.

A summary of the absolute and change from Baseline values in each ECG variable will also be created at each post-Baseline/Screening timepoints by treatment group. The following ECG variables will be summarized: heart rate (bpm), RR interval (ms), PR interval (ms), QRS duration (ms), QT interval (ms), QTcF interval (ms) and QTcB interval (ms).

QTc outliers are defined as QTcF (or QTcB) values following dosing that are greater than 450 ms or are increases from Baseline greater than 30 ms. QTcF and QTcB outliers will be summarized in a dedicated table using the following categories:

- Values >450 ms, >480 ms, >500 ms
- Increase from Baseline of >30 ms, increase from Baseline of >60 ms, increase from Baseline of >90 ms
- Values >450 ms and increases of >30 ms. Values >500 ms and increases of >60 ms

In this table, the number and percentage of study participants who meet the ECG outlier criteria at any assessment post first dose will be summarized.

These three table summaries will cover the overall period on the SS and will present the Placebo/BKZ 160mg Q4W and the BKZ 160mg treatment columns. Baseline Day 1 will serve as Baseline.

A by-study participant listing of all 12-lead ECG data will be provided where QTcF and QTcB outliers will be highlighted.

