Tables on ECG or tuberculosis data	SS (Overall period)	
 Placebo / BKZ 160mg Q4W BKZ 160mg Q4W 	Yes, for all visits up to date of Week 24 visit of last planned participant	Yes, for all visits up to date of Week 52 visit of last planned participant
Tables on PHQ-9 data	SS (Overall period)	
 Placebo / BKZ 160mg Q4W BKZ 160mg Q4W 	Yes, for all visits up to date of Week 24 visit of last planned participant	Yes, for all visits up to date of Week 52 visit of last planned participant
Tables on eC-SSRS data	SS (DB-period only)	
 Placebo BKZ 160mg Q4W 	Yes, for all visits up to Week 16 for each participant	No

This document cannot be used to support and marketing authorization application or variations thereof.

Variable	Analysis Sets (study period)	Treatment groups	Interim Analysis 1	Interim Analysis 2
Type of tables	MS (MP only)	
 • BKZ 160mg Q4W Total 	No	Yes, from Week 16 up to Week 52 for each participant
	SS (Overall period)	
 • BKZ 160mg Q4W Total 	Yes, for all visits up to date of Week 24 visit of last planned participant	Yes, for all visits up to date of Week 52 visit of last planned participant

^a For placebo-randomized study participants, results are determined based on the Baseline Week 16 (See Section 3.3).

Study participants in the Placebo/ BKZ 160mg Q4W treatment group are taking BKZ 160 mg Q4W treatment after Week 16.

The final analysis will occur once last study participant has completed the SFU Visit. The final analysis will consist of a rerun of all listings and all safety summary analyses created for the Week 52 interim analysis but will include data occurring during the SFU period that were not available for the Week 52 interim analysis.

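### QTc outliers are counted at any time over the whole study in a column that joins placebo and later bimekizumab time, and no placebo-controlled QTc outlier table is planned

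*SAP*

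**What the plan says.** SAP Section 10.4.2 plans three ECG tables: investigator interpretation, values and changes by timepoint, and QTc outliers. For outliers, "the number and percentage of study participants who meet the ECG outlier criteria at any assessment post first dose will be summarized". This is an ever/never count per participant, not a count by visit. On period and columns: "These three table summaries will cover the overall period on the SS and will present the Placebo/BKZ 160mg Q4W and the BKZ 160mg treatment columns". The reference value is also fixed: "Baseline Day 1 will serve as Baseline".

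Table 4-3 in Section 4.3.1 agrees. Its row "Tables on ECG or tuberculosis data" has the overall period on the Safety Set only, with no double-blind row.

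On timing, Section 10.4.2 opens with "Since it is only planned to assess electrocardiogram (ECG) at the Screening Visit", yet it goes on to plan summaries at timepoints after Baseline.

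One laboratory summary in Section 10.3 has the same layout. It gives the CTCAE grade "based on the minimum/maximum post-Baseline value, by laboratory variable and treatment group", and "These two tables will be provided on the SS for the overall period, presenting the Placebo/BKZ 160mg Q4W and the BKZ 160mg treatment columns".

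**The concern.** A Placebo/BKZ column does no harm in a by-visit table, because each visit lies on one side of the Week 16 switch. It does matter in an any-time count. A participant with a QTc outlier at Week 12 on placebo and one with an outlier at Week 40 on bimekizumab add equally to the same cell, and the table cannot tell them apart. The neighbouring column is bimekizumab throughout. The only planned comparison of QTc outliers between arms would then be against a group that also received bimekizumab for most of the study, so a real excess would look smaller than it is.

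The Baseline adds to this. Section 10.4.2 derives the ECG Baseline from the Screening assessment, so for switchers an increase of more than 30, 60 or 90 ms after the switch is measured from before the placebo period.

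**Working it through.** The SAP states no QTc outlier rate, so there is no figure of its own to reproduce. The check has two parts.

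**1. How the SAP treats other any-time safety counts**

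- Section 3.7, general rule: double-blind safety data under Placebo and BKZ 160mg Q4W; overall-period safety data under BKZ 160mg Q4W Total.
- Adverse events (Section 10.2), laboratory shift, markedly abnormal and Hy's Law tables (Section 10.3), markedly abnormal blood pressure (Section 10.4.1) and eC-SSRS (Section 10.4.3): each has a double-blind version (Placebo against BKZ) and an overall version under BKZ Total.
- Section 3.3: switchers get a Week 16 Baseline for laboratory shift, markedly abnormal and Hy's Law analyses and for markedly abnormal vital signs. ECG is not included.
- QTc outliers (Section 10.4.2): overall period only, Placebo/BKZ and BKZ columns, Baseline Day 1.

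Among these counts, QTc outliers alone have neither a double-blind version nor a BKZ Total version.

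**2. Size of the dilution, for illustration**

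Inputs from Section 2.3: 16 weeks double-blind, 36 weeks maintenance (16 + 36 = 52), switch at Week 16. Assumptions: a constant low hazard on each treatment, even assessment over time, and true ratio R of bimekizumab to placebo.

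- Expected events per participant, BKZ column: T × R (in units of the placebo hazard).
- Expected events per participant, Placebo/BKZ column: 16 + (T − 16) × R.
- Apparent ratio = T × R / (16 + (T − 16) × R).

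At T = 52:

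- R = 2: 104 / (16 + 72) = 104/88 = 1.18.
- R = 3: 156 / (16 + 108) = 156/124 = 1.26.
- R without limit (no outliers on placebo): 52/36 = 1.44.

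At T = 24, R = 2 gives 48/32 = 1.50 and R = 3 gives 72/40 = 1.80. These understate the dilution at the Week 24 analysis, because Table 4-3 runs the ECG tables to the date of the last planned participant's Week 24 visit, by which time earlier participants have longer follow-up.

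Without the low-hazard approximation, the overall risks are 1 − exp(−52 × hB) for BKZ and 1 − exp(−16 × hP − 36 × hB) for Placebo/BKZ, where hP and hB are the weekly hazards that give assumed 16-week risks:

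- 2% against 4%: ratio 2.00 becomes 1.17.
- 5% against 10%: becomes 25.1% against 29.0%, ratio 1.16. The difference falls from 5.0 to 3.9 points and sits on a much higher background.
- 10% against 20%: ratio 2.00 becomes 1.13.

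**Dependence on the ECG schedule.** ECGs are taken at a few visits, not continuously. With a post-dose ECGs before the switch, b after it, and a low outlier probability at each, the apparent ratio is (a + b) × R / (a + b × R). If b = 0 it equals R, with no dilution. If a = 0 it equals 1, with no placebo data at all. If a = b = 1 and R = 2, it is 4/3 = 1.33.

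**The case against.** The strongest reply is that mixing is not proven. It needs post-dose ECGs on both sides of Week 16, and the SAP does not give those times; the schedule belongs to the protocol. If all post-dose ECGs precede the Week 16 dose, the table is already a clean placebo comparison. If all follow it, a double-blind table would be empty. This stands, and it is why the size above is only illustrative. It does not defend the layout, which is fixed without regard to the schedule.

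A reader might infer that the two columns cannot show a drug effect at all. The arithmetic does not support that: the contrast is diluted, not removed, unless there are no ECGs on placebo.

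A reader might also extend the gap to worst CTCAE grades. That does not hold. The shift table in Section 10.3 runs from Baseline grade to worst later grade for largely the same parameters. It is presented for the double-blind period as Placebo against BKZ, as are the Grade 3 and above tables and Hy's Law. The worst-grade summary shares the mixed column, but the placebo comparison exists elsewhere.

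Other points are fair but partial:

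- Section 3.1 defines the Placebo/BKZ column openly. A clear label does not separate pooled counts.
- The by-timepoint ECG tables give a placebo-only column at any double-blind ECG. They show means and interpretation, not outliers.
- The participant listing highlights QTc outliers, and ECG dates are recorded, so outliers can be assigned to a period by hand. A listing is not a planned comparison.
- ECG is an other safety variable, QTc is not among the safety topics of interest, and no test is planned. This limits the importance.

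**Conclusion.** The point holds for QTc outliers. The SAP fixes an any-time count over the overall period in a column that can combine placebo and bimekizumab findings, and it plans no placebo-controlled QTc outlier table. This departs from its rule in Section 3.7 and from its handling of comparable safety counts.

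If ECGs fall on both sides of the switch, the contrast is diluted. A true ratio of 2 would show as about 1.18 over 52 weeks, with a ceiling of 1.44, given constant low hazards and even assessment. Under other schedules the result ranges from no dilution to no contrast, so the actual size cannot be judged until the statement that ECG is planned only at Screening is reconciled with the post-Baseline ECG tables. The laboratory worst-grade summary is a minor consistency point.

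**What to change.** In SAP Section 10.4.2, replace the single QTc outlier table with the two-table layout already used for markedly abnormal values:

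1. Double-Blind Treatment Period on the Safety Set, Placebo against BKZ 160mg, using post-dose ECGs before the first maintenance dose.
2. Overall period under BKZ 160mg Q4W Total, using only ECGs after the first bimekizumab dose. For switchers, Baseline is the last ECG before that dose, or Screening if there is none later. Add this to Section 3.3.

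Add a double-blind row for ECG outliers to Table 4-3. Reconcile the statement on when ECGs are planned with the post-Baseline tables, and state the post-dose ECG timepoints or cite the protocol schedule. If no ECG falls between the first dose and the Week 16 dose, say that a placebo comparison is not possible. For the worst-grade laboratory summary, a footnote pointing to the double-blind shift table is enough.

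The cost is SAP wording and one extra table version built on an existing layout, with small counts in each table. No endpoint or data collection changes. For switchers with no ECG on placebo, Screening remains the only reference, so re-baselining gains nothing for them.
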